9 WITHDRAWAL OF SUBJECTS

It is under the responsibility of the Principal Investigator in each IG-IBD Centre who has in charge the patient to withdraw her/him from the study and to advise both the Study Coordinator and Data Manager specifying the reason/s. The impossibility to harvest mucosal biopsies is considered a criterion for subject withdrawal. In this case, the patient's data will be removed from the database, but considered when assessing patient disposition. The development of malignancy or death are primarily considered as evolution of the underlying disease. In addition, a patient has the right to withdraw from the study at any time for any reason. Subjects who withdraw their consent are considered withdrawn from the study. The Principal Investigator has the right to terminate participation of any patient if it is deemed in the patient's best interest and if she/he develops severe psychiatric or neurological disorders. The reason and circumstances for premature discontinuation must be reported in the patient's electronic case report form (eCRF). This means that a patient may be withdrawn in every phase of the trial, from the inclusion to any time of the follow-up period. In summary, reasons of withdrawal include, but are not limited, to the following:

- Patient's decision,
- Withdrawal of patient consent to participate in the study,
- Physician's decision based on patient's well-being.

For any subject discontinuing the study the Principal Investigator should before do the following:

- Complete the eCRF, indicating in the final visit, the date of termination and the reason for discontinuing the study as well as the protocol deviation section, with all data not corresponding to a formal visit filled in the Early Termination visit.

In patients who do not come back for the scheduled study visits, documented efforts should be performed to convince she/he to continue attending study visits and if unsuccessful, at least the exact reason(s) should be obtained for their discontinuation and any adverse event associated to it should be recorded.

The patient will be replaced if her/his mucosal specimens are not available for the full analyses.

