5.2.2 Secondary endpoint

a- Comparison of the presence of EBV infection in the cohort of patients suffering from UC and divided into the following subgroups: a) new diagnosis; b) responders to conventional therapies; c) non-responders to conventional therapies, in order to unravel whether it is a bystander or causative of the onset/relapse of the disease and whether it is responsible for refractoriness to standard of care.

b- Evaluation of the diagnostic ability in detection of EBV infection of ISH performed on mucosal specimens with respect to qRealTime-PCR.

c- Evaluation of the diagnostic ability in detection of EBV infection between qRealTime-PCR performed on peripheral blood samples with respect to mucosal specimens.

d- Evaluation of association between mucosal/blood viral load and mucosal damage as endoscopically assessed (see paragraph 5).

e- Evaluation of association between clinical index of UC activity and EBV infection.

f- Evaluation of association between steroid therapy (absent, previous or current) and EBV infection.

g- Evaluation of association between immunosuppressive therapy (absent, previous or current) and EBV infection.

h- Evaluation of association between biological therapy (absent, previous or current) and EBV infection.

i- Evaluation of the prognostic role of EBV infection on the 6 and 12 months outcome (colectomy / number of hospitalization / cause of hospitalization).

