7.1 General design

- ❖ *Type:* cross-sectional study with a longitudinal component.
- ❖ *Description of the exposure of interest:* EBV infection, defined as isolation of the EBV or detection of viral proteins or nucleic acids in any body fluid or tissue specimens.
- ❖ *Description of the matching factor(s) and how the matching will be done:* Center, sex- and age (5 year classes)-matching will be performed among the IBD patients and concomitant non-IBD control subjects.
- ❖ *Methods used to minimize bias.* The assessment of EBV infection through qRealTime-PCR, histology or ISH as primary endpoint is *per se* unbiased due to standardization and reproducibility of the techniques applied. Also calculation of clinical and endoscopic indexes of activity are routinely applied in IG-IBD centres. Moreover, the measurement of exploratory endpoints will be assessed by blinded technicians, whereas monitoring of patients' outcome will be performed by the local Principal Investigator.
- ❖ *Describe the strategy/process by which participants will be recruited, screened, and enrolled in the study.* All cases admitted at each IG-IBD center that agrees to participate in this study will be screened for inclusion. All enrolled cases undergo lower endoscopy with mucosal sampling from both inflamed and non-inflamed mucosa in each IBD patient and from healthy mucosa in each control subject, as part of their diagnostic workup for disease diagnosis, relapse or follow-up. Patients' assessment includes: clinical examination, body mass index calculation, evaluation of smoking habits and stratification according to the Montreal classification (44), routine laboratory tests, and calculation of clinical [SCCAI (45)] and endoscopic [UCEIS (46,47)] indexes of activity.
- ❖ All enrolled cases also undergo peripheral blood harvest. Quantitation of viral DNA load will be performed on both peripheral blood samples and whole mucosal specimens by means of qRealTime-PCR (50). In addition, mucosal specimens will be also evaluated by ISH.

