l) The Informed Consent Form will include a statement by which the patient allows the Sponsor's duly authorised personnel, the IEC, and the regulatory authorities to have direct access to source data which supports the data on the eCRF (e.g., patient's medical file, appointment books, original laboratory records, etc.). These personnel, bound by professional secrecy, will not disclose any personal identity or personal medical information.

m) Data collection and study report form monitoring. All data obtained for this study will be entered into a regulation compliant Data Management System. Data will be recorded with an Electronic Data Capture system using eCRFs. Specifically, the Electronic Data Capture system will be based on the IGIBDReg platform. IGIBDReg is a novel workflow methodology and software tool that expedites the electronic collection of research data from a single site or multi-site clinical research study. The study database will be resident on OVH server (<https://www.ovhcloud.com/>) as required by European Certification

n) Procedure to account for missing or spurious data. In case of missing clinical assessment at follow-up visit, the last observation carried forward from the latest earlier visit will apply, while in case of missing clinical, endoscopic and histologic data by month 12, the evaluation of outcome will not be possible. We expect to have 10% patients on drop-out. IGIBDReg provides section to recording missing or N/A information.

o) Procedure to account for protocol deviations. Generally, a protocol deviation is not imperative for patient withdrawal. Before the statistical analysis begins, the protocol deviations must be taken into account for the analysis. The mandatory withdrawal reasons will be considered as major protocol deviations. Other protocol deviation will be classified as minor protocol deviation. Additionally, the lack of compliance with any of the inclusion/exclusion criterion, either identified before or after enrolment into the study, will be considered as major protocol deviation. Any protocol deviation must be recorded in the eCRF (specific section in IGIBDReg). Once the study has begun, any modification of the protocol deviation will be specified in the statistical analysis plan. This will be done before closing the database.

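### Section 9 does not require colectomy and hospitalisation to be recorded after an investigator ends a patient's participation, so censoring in the prognostic analysis (EP2i) may be informative

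*Protocol*

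**What the plan says.** Section 7 describes a study without drug or medical device. Section 9 nevertheless gives the investigator in charge of the patient a discretionary power: the Principal Investigator "has the right to terminate participation of any patient if it is deemed in the" patient's best interest. The sentence goes on to severe psychiatric or neurological disorders, but the list of reasons that follows gives "Physician's decision based on patient's well-being" on its own. The section adds that "a patient may be withdrawn in every phase of the trial, from the inclusion to any time of the follow-up period".

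Two rules in Section 9 govern what is then recorded:

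- For any subject who discontinues, the site completes the eCRF with the termination date, the reason and the deviation section, and enters data outside formal visits in an Early Termination visit.
- For patients who stop attending, the site tries to bring them back. Failing that, "at least the exact reason(s) should be obtained for their discontinuation and any adverse event associated to it should be recorded".

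Neither rule mentions events after termination. The endpoint that depends on them is in Section 5.2.2 (i): "Evaluation of the prognostic role of EBV infection on the 6 and 12 months outcome", meaning colectomy and the number and cause of hospitalisations. Section 8.2 analyses it by Cox and Poisson regression.

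Section 7.1 states that "monitoring of patients' outcome will be performed by the local Principal Investigator". It claims blinding only for the technicians who measure exploratory endpoints. Section 10 e) gives Principal Investigators access to the database.

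Section 10 n) expects 10% drop-out. For a clinical assessment missing at a follow-up visit, "the last observation carried forward from the latest earlier visit will apply". If clinical, endoscopic and histologic data are missing by month 12, outcome is treated as not evaluable.

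**The concern.** Cox regression takes censoring to be unrelated to the coming event, given the covariates. A decision to end participation for well-being can plausibly fall on a patient who is getting worse, and such patients are the ones at risk of colectomy and admission. With no study product to stop, ending participation here means only ending visits, sampling and data collection. The protocol does not separate these.

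A link between withdrawal and EBV status does not need anyone to know the EBV result. Section 8.1 expects EBV in about 50% of non-responders and about 10% of responders, so withdrawal driven by refractoriness would also be associated with EBV. Nothing in the protocol rules out the more direct route either, because the investigator is not stated to be blinded.

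At stake is the study's only prognostic endpoint. Few events are likely, so a handful of uncollected ones could move the estimate noticeably. An analysis plan cannot recover events that sites were never told to record.

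**Working it through.** The protocol gives no event rates or effect size for EP2i, so there is no planned figure to reproduce. Its one relevant number is the 10% drop-out, or 10 of 100 UC patients. Everything below marked as assumed is illustration.

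**Assumed inputs.** Event risk r is 0.30 in EBV-positive and 0.15 in EBV-negative patients, so the true RR is 2.0. Let *we* be the proportion of patients heading for an event who are withdrawn first, and *wn* the same proportion among the others.

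**Formulas.** The protocol does not settle how withdrawn patients are treated, so two treatments are shown.
- Dropped: observed risk = r(1−we) / [r(1−we) + (1−r)(1−wn)]
- Counted as event-free: observed risk = r(1−we)

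Censoring at the withdrawal date credits follow-up time between these two.

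**Scenario A: we = 0.30 in EBV-positive; 0.05 for everyone else.**
- Dropped, EBV-positive: 0.30×0.70 / (0.30×0.70 + 0.70×0.95) = 0.210/0.875 = 0.240. EBV-negative: 0.150. RR = 1.60.
- Event-free: 0.210 against 0.15×0.95 = 0.1425. RR = 1.47.
- As hazard ratios, from −ln(1−risk): true 0.357/0.163 = 2.19; dropped 0.274/0.163 = 1.69; event-free 0.236/0.154 = 1.53.
- Withdrawal is 0.30×0.30 + 0.70×0.05 = 12.5% of EBV-positive and 5% of EBV-negative patients. The total is 8.75% if half are EBV-positive and 7.25% if 30% are. Both are within the stated 10%.

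**Scenario B: we = 0.30, wn = 0.05 in both groups.**
- Dropped: 0.240 against 0.105/(0.105 + 0.8075) = 0.115. RR = 2.09.
- Event-free: 0.210/0.105 = 2.0.
- The ratio barely moves, but both absolute risks are understated.

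**Scenario C: we = 0.30 in EBV-negative only; 0.05 for everyone else.**
- Dropped: 0.300/0.115 = 2.61. Event-free: 0.285/0.105 = 2.71. The bias now runs away from no effect.

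**Check with counts (assumed).** Take 100 UC patients, all followed, 30 EBV-positive, with colectomy risk 20% against 10%: 6 and 7 events, true RR 2.0. Withdrawn patients are dropped.

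| Events falling after withdrawal | Observed risks | RR |
|---|---|---|
| none | 6/30 vs 7/70 | 2.00 |
| half of EBV-positive events (3) | 3/27 = 0.111 vs 0.100 | 1.11 |
| half of EBV-negative events (3.5) | 0.200 vs 3.5/66.5 = 0.053 | 3.80 |

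Appendix 3 schedules follow-up for active UC only, so the real counts would probably be smaller and each lost event would weigh more.

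**The case against.** **Data are captured up to termination.** A reader might infer that after an investigator-decided withdrawal only the reason and related adverse events are collected. That is not what Section 9 says. The rule is for patients who stop attending, and it is a minimum. Investigator-terminated patients get a completed eCRF and an Early Termination visit. This stands: the gap lies after termination.

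**The investigator is not shown to know the EBV result.** A reader might call the investigator EBV-unblinded. Assays are centralised, no section says that results go back to sites during follow-up, and database access does not show when results are entered. This also stands. All that can be said is that no blinding is stated.

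**Carry-forward need not mean no colectomy.** A reader might infer that a withdrawn patient is recorded as colectomy-free. Section 10 n) speaks of missing clinical assessments and, in the same sentence, of outcome that cannot be evaluated. Carrying forward an event-free status is one reading; excluding the patient is another. The text leaves this open.

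**Withdrawal is not shown to follow prognosis.** Section 9 does not name worsening colitis as a reason, and a well-being clause is an ordinary protection. That is why the bias is a possibility and not a demonstrated result.

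**Censoring rules can sit in an analysis plan.** This is true of the censoring date. It is not true of the instruction to collect the events. Clinical charts and medical files are already source data (Section 10 d), but their use after withdrawal is not stated.

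**Conclusion.** The gap is real and should be closed. The protocol allows discretionary withdrawal during follow-up by the person who monitors outcome, and has no provision for recording colectomy or hospitalisation afterwards. EP2i needs both at 6 and 12 months. If withdrawal is related to prognosis, censoring is informative.

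In the illustrations a true RR of 2.0 appears as about 1.5 to 1.6 under selective loss of EBV-positive events, stays at 2.0 to 2.1 under equal withdrawal, and rises to about 2.6 to 2.7 under selective loss of EBV-negative events. These figures rest on assumed risks and withdrawal patterns; the protocol supplies neither. A reader might infer a bias towards no effect. The documents do not support any one direction, nor do they show that bias will occur. The effect is confined to secondary endpoint EP2i. The cross-sectional prevalence comparison is not touched by this mechanism.

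**What to change.** **Section 9.** Separate stopping study visits and sampling from stopping outcome collection. State that, unless the patient withdraws consent to the use of data, the date of colectomy, the date and cause of each hospitalisation, and the date of last contact are still taken from the centre's routine records at month 6, and at month 12 where available.

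**Section 10 n).** State that carry-forward does not apply to colectomy or hospitalisation, and that patients lost to follow-up are censored at last documented contact and not excluded.

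**Cost.** A protocol amendment, and a chart check for about 10 patients (10% of 100), most of whom should still be in routine care at the participating centres. Section 11.3 already has patients told that their records may be reviewed; the consent wording must also cover review after visits stop. The change concerns data collection only and alters no clinical rule.

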10 FORMS AND PROCEDURES FOR COLLECTING DATA AND DATA MANAGING

a) Quality and Consistency controls. Electronic case report forms (eCRF) will be filled directly by the Principal Investigators. Prior to obtaining the clean file, checks of consistency of inclusion/exclusion criteria, clinical assessment, visit dates, compliance, concomitant treatment, outcome, and withdrawal information will be performed. Data query forms will be generated to the investigator in order to clarify the data inconsistencies through the source data verification.

b) Data Management Plan. A validation plan is set-up according to the protocol requirements, which describes the validation rules to be applied. Actions that should be taken in case of data abnormalities are detailed. In case of missing values, out of range values, data inconsistencies or values that fail logical checks, correction forms (queries) are edited and transmitted to the investigator for clarification.

c) Database. A database will be created in order to collect all clinical and other data from the present study. The data management will be provided by the Service of Clinical Epidemiology & Biometry of the I.R.C.C.S. Policlinico San Matteo Foundation (Pavia, Italy). The IGIBDReg platform will be used (<https://igibdreg.ibismed.cloud/>) .

d) Source documents. Evaluation of all clinical parameters, including laboratory tests, body mass index, and symptoms will be performed at the IG-IBD Centre where the patient is in charge and shared with the Study Coordinator. Study data will be collected on source documents. Each Principal Investigator is responsible for assuring that collected data are complete and accurate. Source documentation (the point of initial recording of a piece of data) will support data collected on the eCRF. The eCRF is the primary data collection instrument for the study. Source documents include all recordings of observations or notations of clinical activities and all reports and records necessary

for the evaluation and reconstruction of the clinical study (see below). Completed eCRF data will be entered into the database within a week of the patient visit being completed. According to the ICH guidelines on GCP, the Data Manager must check the eCRF entries against the source documents, except for the pre-identified source data directly recorded in the eCRF.

Source Data

- *Clinical Charts,*
- *Patients medical files,*
- *Signed Informed Consent Forms,*
- *On-line test results (especially if only held electronically),*
- *Samples log.*

e) Database Access. Access to the eCRF database will be allowed to the Principal Investigators, data managers, members of the Steering Committee and IGIBD Scientific Committee. Any entry in the database will be traceable through its identification and date. Audit trail of data changes will be assured.

f) Data reported in the eCRFs should be consistent with and substantiated by the subject's medical record and original source documents. The final, completed eCRF Casebook for each subject will be electronically signed and dated by the investigator of the IG-IBD Centre to signify that the Investigator has reviewed the eCRF and certifies it to be complete and accurate within a month.

g) Data Queries. Data query forms will be generated to the Coordinator Investigator in order to clarify the data inconsistencies through the source data verification. Only then and after all detected errors, inconsistencies or doubts cleared, will the database declared a clean file and protected accordingly. IGIBDReg integrates a query management system.

h) All data entry, modification or deletion will be recorded automatically in an electronic audit trail. The investigators will retain all copies of the eCRF in the relevant sections of their Investigator Site File with any required anonymised background information from the medical records as required.

i) Clean File. A clean file will be created and registered, to which further changes will be disallowed. The database lock report will be generated which includes the eligibility of patients.

j) Data Quality Assurance. Periodic monitoring will be made by remote for source data verification, and to check compliance with the protocol, GCP and applicable regulatory requirements by the Data Manager. Quality control steps will be taken for the analytical protocol, results, and report.

k) The Trial Statistician will retain the final eCRF data and audit trail as permanent records of the study. A copy of all completed eCRFs will be provided to the investigators. Study document will be retained for 10 years after the completion of the protocol.

l) The Informed Consent Form will include a statement by which the patient allows the Sponsor's duly authorised personnel, the IEC, and the regulatory authorities to have direct access to source data which supports the data on the eCRF (e.g., patient's medical file, appointment books, original laboratory records, etc.). These personnel, bound by professional secrecy, will not disclose any personal identity or personal medical information.

m) Data collection and study report form monitoring. All data obtained for this study will be entered into a regulation compliant Data Management System. Data will be recorded with an Electronic Data Capture system using eCRFs. Specifically, the Electronic Data Capture system will be based on the IGIBDReg platform. IGIBDReg is a novel workflow methodology and software tool that expedites the electronic collection of research data from a single site or multi-site clinical research study. The study database will be resident on OVH server (<https://www.ovhcloud.com/>) as required by European Certification

n) Procedure to account for missing or spurious data. In case of missing clinical assessment at follow-up visit, the last observation carried forward from the latest earlier visit will apply, while in case of missing clinical, endoscopic and histologic data by month 12, the evaluation of outcome will not be possible. We expect to have 10% patients on drop-out. IGIBDReg provides section to recording missing or N/A information.

o) Procedure to account for protocol deviations. Generally, a protocol deviation is not imperative for patient withdrawal. Before the statistical analysis begins, the protocol deviations must be taken into account for the analysis. The mandatory withdrawal reasons will be considered as major protocol deviations. Other protocol deviation will be classified as minor protocol deviation. Additionally, the lack of compliance with any of the inclusion/exclusion criterion, either identified before or after enrolment into the study, will be considered as major protocol deviation. Any protocol deviation must be recorded in the eCRF (specific section in IGIBDReg). Once the study has begun, any modification of the protocol deviation will be specified in the statistical analysis plan. This will be done before closing the database.

Management of biological samples. The histologic slides will be stored at room temperature in a dedicated rack on long-term at the Pathology Unit of each referral Centre, except for a couple of sections that will be sent to the Service of Pathology of the ASST Spedali Civili in Brescia for centralized examination (Doctor [name]). In addition, snap-frozen mucosal and whole

peripheral blood samples will be collected and stored in liquid nitrogen tanks of each Centre participating in the study and then sent to the Laboratory of Molecular Virology of the I.R.C.C.S. Policlinico San Matteo Foundation (Pavia) for viral load centralized detection ([name]). These biological samples will be used for qRealTime-PCR assay and will be destroyed once processed. The Principal Investigator of each Centre who has in charge the patient is responsible for the appropriate storage and has full access to the biological samples that are labelled with the date, the patient's code and the trial number. No further researchers will have access to these samples.

